3.1 Trial design

An investigator-initiated, pragmatic, international, multicentre, randomised, blinded, parallel-group trial of pantoprazole versus placebo.

3.2 Randomisation

Patients will be screened for enrolment at admission to the ICU (see section 3.5). This will be ensured through implementation of trial methodology at trial sites.

1:1 randomisation will be centralised and web-based randomisation according to the computer-generated allocation sequence list, stratification variables (site and active hematologic cancer), and varying block size. The allocation sequence list will be unknown to the investigators to allow immediate and concealed allocation to intervention with pantoprazole or placebo. Each patient will be allocated a unique patient-screening number.

3.3 Blinding

Pantoprazole is preserved as a powder in a glass vial and needs to be dissolved in 10 ml of isotonic saline. The powder is momentarily dissolved with no need of shaking the vial. The solution is colourless and cannot be distinguished from saline. When the glass vial is masked,

it is not possible to determine whether the vial contains powder or is empty. The placebo will be an empty vial. Saline (10 ml) will be added to the empty vial in the same way as for the experimental intervention.

The blinding of the trial medication will be a white label covering the whole vial including the bottom and the neck. The label will contain the required information of the trial drugs. The top of the placebo vial will be identical with the vial of the active drug.

The allocated trial medication will be blinded to the clinical staff caring for the patient, to the patient, investigators, outcome assessors, and the data manager. The statistical analysis of the trial will be blinded with the intervention groups coded as, e.g., X and Y. Based on this blinded analysis two conclusions will be drawn: one assuming X is the experimental group and Y is the control group, and one conclusion assuming the opposite. Two abstracts will be written and accepted by the author group. After this, the blinding will be broken.

The members of the Data Monitoring and Safety Committee (DMSC) will remain blinded unless 1) they request otherwise or 2) one of the two interim analyses has provided strong indications of one intervention being beneficial or harmful (a charter for the independent DMSC is attached in *appendix 3*).

3.3.1 Unblinding

3.3.1.1 An individual

The intervention may be unblinded for individual patients if deemed necessary by the clinician or investigator for the treatment and safety of the patient.

In case of a suspected unexpected serious adverse reaction (SUSAR) the sponsor (or delegated party) shall break the blinding in order to judge the 'expectedness' and therefore the occurrence of a SUSAR (according to the summary of product characteristics), and report it to the authorities accordingly. See section 8 for more information.

3.3.1.2 Procedure

If the intervention for an individual patient needs to be unblinded during the trial, the treating physician shall contact Copenhagen Trial Unit (CTU), who will reveal the allocated trial intervention (pantoprazole or placebo). This can be done by telephone at all hours, any day of the week. If the investigator needs immediate unblinding of the trial medication, this can be done by removing the white label covering the glass vial.

3.5 Participant timeline

We will strive to enrol patients as soon as they fulfil the inclusion criteria. Patients will be allocated to either intravenous pantoprazole or placebo once daily and will continue the allocated intervention until death in the ICU or discharge from the ICU with a maximum of 90 days after randomisation.

If the patient is readmitted to the ICU within 90 days after randomisation the patient should continue the allocated treatment.

4. Selection of participants

All patients referred to a participating clinical trial site will be considered for participation.

Patients will be eligible, if they fulfil all of the inclusion criteria and none of the exclusion criteria listed below (see also *appendix 4*)

4.1 Inclusion criteria

- Acute admission to the ICU **AND**
- Aged ≥ 18 years **AND**
- One or more of the following risk factors:
 - Shock (continuous infusion with vasopressors or inotropes, systolic blood pressure < 90 mmHg, mean arterial blood pressure < 70 mmHg or lactate > 4 mmol/l)
 - Acute or chronic intermittent or continuous renal replacement therapy
 - Invasive mechanically ventilation which is expected to last > 24 hours. When in doubt of the forecast, the patient should be enrolled
 - Coagulopathy (platelets $< 50 \times 10^9/l$ or international normalized ratio (INR) > 1.5 or prothrombin time (PT) > 20 seconds) documented within the last 24 hours
 - Ongoing treatment with anticoagulant drugs (prophylaxis doses excluded)
 - History of coagulopathy (platelets $< 50 \times 10^9/l$ or INR > 1.5 or PT > 20 seconds within 6 months prior to hospital admission
 - History of chronic liver disease (portal hypertension, cirrhosis proven by biopsy, computed tomography (CT) scan or ultrasound, history of variceal bleeding or hepatic encephalopathy in the past medical history)

4.2 Exclusion criteria

- Contraindications to PPI
- Ongoing treatment with PPI and/or H2RA on a daily basis
- GI bleeding of any origin during current hospital admission
- Diagnosed with peptic ulcer during current hospital admission
- Organ transplant during current hospital admission
- Withdrawal from active therapy or brain death
- Fertile woman with positive urine human chorionic gonadotropin (hCG) or plasma-hCG
- Consent according to national regulations not obtainable

4.3 Participant discontinuation and withdrawal

4.3.1 Discontinuation and withdrawal at the choice of the participant

The procedure of handling withdrawal of consent from a patient will follow national regulations and will be described by each participating country.

The Danish procedure:

A patient, who no longer wishes to participate in the trial, can withdraw his/her consent at any time without need of further explanation, and without consequences for further treatment.

Patients may be withdrawn from the trial at any time if consent is withdrawn by the person(s), who has given proxy-consent.

In order to limit the amount of missing data we plan to collect as much data from each patient as possible. Therefore, if possible, the investigator will ask the patient which aspects of the trial, he/she wishes to withdraw from:

- receiving the trial intervention only (allowing for all data registration and follow-up)

OR

- receiving the trial intervention AND further registration of daily data and/or follow-up

Only the patient can demand deletion of already registered data and only if the patient did not consent previously. If so, data will be deleted and a new patient will be randomised to obtain the full sample size.

4.3.2 Discontinuation and withdrawal at the choice of the investigator

A patient can be discontinued from the trial intervention by the investigator at any time, if:

- the patient experiences intolerable adverse reactions suspected to be related to the trial intervention

AND/OR

- the patient develops upper GI bleeding or another condition where the clinician finds indication for treatment with PPI or H2RA. The intervention will be stopped and the patient will receive relevant treatment.

In these cases, the collection of data will continue and the follow-up will be conducted. The patient will remain in the intention-to-treat population if the allocated trial intervention has been given.

If an ineligible patient is randomised by mistake and the trial intervention has not been given, data will be deleted (logged as a flawed randomisation) and a new patient will be randomised [60]. If the intervention has been given, the patient will continue in the trial and in the intention-to-treat population.

If the patient experiences a serious adverse reaction (SAR) or a suspected unexpected serious adverse reaction (SUSAR) the trial intervention will be stopped; data registration will continue (see section 8).

Patients who are transferred to another ICU will be regarded as discharged from the ICU unless the new ICU is an active SUP-ICU trial site. In any case, patients transferred to another ICU will be followed up for the primary outcome measure and as many of the secondary outcome measures as possible.

5. Selection and trial sites and personnel

5.1 Trial sites and setting

Trial sites will be ICUs [61] in Europe. Trial sites are listed in the section 'Administrative information'. This section will be updated during the trial.

5.2 Trial personnel

All clinicians caring for patients in participating ICUs will be eligible to screen patients and perform the interventions.

All participating ICUs will receive written and oral instructions about the trial procedures. A 24-hour hotline will be available for questions.

6. Trial interventions

6.1 Experimental intervention

To ensure systemic uptake of pantoprazole all patients randomised to the experimental group will be given intravenous pantoprazole 40 mg upon randomisation and hereafter once daily. The intervention period will be from randomisation until discharge from the ICU or death in the ICU. If the patient is readmitted, the allocated intervention should be continued until final discharge from the ICU or the end of the 90-day trial period.

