History of coagulopathy: coagulopathy defined as platelets < 50 x 10⁹/l AND/OR INR > 1.5 AND/OR PT > 20 seconds within 6 months prior to hospital admission.

History of chronic liver disease: portal hypertension, cirrhosis proven by biopsy, computed tomography (CT) scan or ultrasound, history of variceal bleeding or hepatic encephalopathy in the past medical history

Definition of exclusion criteria

Contraindications to proton pump inhibitors (PPI): any history of intolerance to PPI or additives or treatment with atazanavir (HIV medication)

Ongoing treatment with PPI and/or histamine-2-receptor antagonists (H2RA): ongoing is defined as treatment not being discontinued at ICU admission. If clinicians do not find indication for continuation of treatment with PPI/H2RA during ICU stay, the patient will be eligible for inclusion.

GI bleeding during current hospital admission: GI bleeding of any origin (both upper and lower) documented in the patient charts

Peptic ulcer: peptic ulcer confirmed by endoscopy or other method during current hospital admission

Organ transplant: any kind of organ transplant during current hospital admission.

Withdrawal from active therapy or brain death: patients where withdrawal or brain death is documented in the patient charts

Known pregnancy: fertile woman with positive urine human chorionic gonadotropin (hCG) or plasma-hCG

Consent not obtainable according to national regulations: patients where the clinician or investigator is unable to obtain necessary consent before inclusion of the patient according to the national regulations

Definition of baseline variables

Sex: the genotypic sex of the patient

Age: defined in inclusion criteria

Date of admission to hospital: the date of admission to the first hospital the patient was admitted to during the current hospital admission

Elective surgery: surgery during current hospital admission scheduled 24 hours or latter in advance

Emergency surgery: surgery during current hospital admission that was added to the operating room schedule 24 hours or less prior to surgery

Medical admission: when no surgery has been performed during current hospital admission OR surgery has been performed more than 1 week prior to ICU admission

Treatment with anticoagulants at hospital admission and at ICU admission: anticoagulants are defined in inclusion criteria

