4.2 Posology and method of administration

This medicine should be administered by a healthcare professional and under appropriate medical supervision.

The intravenous administration of pantoprazole is recommended only if oral application is not appropriate. Data are available on intravenous use for up to 7 days. Therefore as soon as oral therapy is possible, treatment with pantoprazole i.v. should be discontinued and 40 mg pantoprazole p.o. should be administered instead.

Posology

Gastric and duodenal ulcer, reflux oesophagitis

The recommended intravenous dose is one vial of pantoprazole (40 mg) per day.

Zollinger-Ellison Syndrome and other pathological hypersecretory conditions

For the long-term management of Zollinger-Ellison Syndrome and other pathological hypersecretory conditions patients should start their treatment with a daily dose of 80 mg of pantoprazole i.v. Thereafter, the dosage can be titrated up or down as needed using measurements of gastric acid secretion to guide. With doses above 80 mg daily, the dose should be divided and given twice daily. A temporary increase of the dosage above 160 mg pantoprazole is possible but should not be applied longer than required for adequate acid control.

In case a rapid acid control is required, a starting dose of 2 x 80 mg of pantoprazole i.v. is sufficient to manage a decrease of acid output into the target range (<10 mEq/h) within one hour in the majority of patients.

Special populations

Paediatric population

The experience in children is limited. Therefore, pantoprazole i.v. is not recommended for use in patients below 18 years of age until further data become available.

Hepatic impairment:

A daily dose of 20 mg pantoprazole (half a vial of 40 mg pantoprazole) should not be exceeded in patients with severe liver impairment (see section 4.4).

Renal impairment:

No dose adjustment is necessary in patients with impaired renal function.

Elderly

No dose adjustment is necessary in elderly patients.

Method of administration

A ready-to-use solution is prepared in 10 ml of sodium chloride 9 mg/ml (0.9%) solution for injection. For instructions for preparation see section 6.6. The prepared solution may be administered directly or may be administered after mixing it with 100 ml of 9 mg/ml (0.9%) sodium chloride injection, or 50 mg/ml glucose (5%) solution for injection.

After preparation the solution must be used within 12 hours (see section 6.3).

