4.4 Special warnings and precautions for use

In presence of alarm symptoms

In the presence of any alarm symptom (e.g. significant unintentional weight loss, recurrent vomiting, dysphagia, haematemesis, anaemia or melaena) and when gastric ulcer is suspected or present, malignancy should be excluded, as treatment with pantoprazole may alleviate symptoms and delay diagnosis.

Further investigation is to be considered if symptoms persist despite adequate treatment.

Hepatic impairment

In patients with severe liver impairment, the liver enzymes should be monitored during therapy. In the case of a rise in the liver enzymes, the treatment should be discontinued (see section 4.2).

Co-administration with atazanavir

Co-administration of atazanavir with proton pump inhibitors is not recommended (see section 4.5). If the combination of atazanavir with a proton pump inhibitor is judged unavoidable, close clinical monitoring (e.g. virus load) is recommended in combination with an increase in the dose of atazanavir to 400 mg with 100 mg of ritonavir. A pantoprazole dose of 20 mg per day should not be exceeded.

Gastrointestinal infections caused by bacteria

Pantoprazole, like all proton pump inhibitors (PPIs), might be expected to increase the counts of bacteria normally present in the upper gastrointestinal tract. Treatment with pantoprazole may lead to a slightly increased risk of gastrointestinal infections caused by bacteria (e.g. *Salmonella* and *Campylobacter* and *C.difficile*).

Sodium

This medicinal product contains less than 1 mmol (23 mg) sodium per dose, i.e. essentially “sodium-free”.

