4.9 Overdose

There are no known symptoms of overdose in man.

Systemic exposure with up to 240 mg administered intravenously over 2 minutes was well tolerated. As pantoprazole is extensively protein bound, it is not readily dialysable.

In case of overdose with clinical signs of intoxication, apart from symptomatic and supportive treatment, no specific therapeutic recommendations can be made.

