5. PHARMACOLOGICAL PROPERTIES

5.1 Pharmacodynamic properties

Pharmacotherapeutic group: Proton pump inhibitors, ATC code: A02BC02.

Mechanism of action

Pantoprazole is a substituted benzimidazole which inhibits the secretion of hydrochloric acid in the stomach by specific blockade of the proton pumps of the parietal cells.

Pantoprazole is converted to its active form in the acidic environment in the parietal cells where it inhibits the H⁺/K⁺-ATPase enzyme i.e. the final stage in the production of hydrochloric acid in the stomach. The inhibition is dose-dependent and affects both basal and stimulated acid secretion. In most patients, freedom from symptoms is achieved within 2 weeks. As with other proton pump inhibitors and H₂ receptor inhibitors, treatment with pantoprazole reduces acidity in the stomach and thereby increases gastrin in proportion to the reduction in acidity. The increase in gastrin is reversible. Since pantoprazole binds to the enzyme distal to the cell receptor level, it can inhibit hydrochloric acid secretion independently of stimulation by other substances (acetylcholine, histamine, gastrin). The effect is the same whether the product is given orally or intravenously.

The fasting gastrin values increase under pantoprazole. On short-term use, in most cases they do not exceed the upper limit of normal. During long-term treatment, gastrin levels double in most cases. An excessive increase, however, occurs only in isolated cases. As a result, a mild to moderate increase in the number of specific endocrine (ECL) cells in the stomach is observed in a minority of cases during long-term treatment (simple to adenomatoid hyperplasia). However, according to the studies conducted so far, the formation of carcinoid precursors (atypical hyperplasia) or gastric carcinoids as were found in animal experiments (see section 5.3) have not been observed in humans.

An influence of a long term treatment with pantoprazole exceeding one year cannot be completely ruled out on endocrine parameters of the thyroid according to results in animal studies.

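### The flat 40 mg daily dose exceeds the appended 20 mg limit for eligible patients with severe liver impairment, and the plan states no dose rule, exclusion or reason

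*Combined protocol and SAP*

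**What the plan says.** **Dose.** Section 6.1 of the protocol sets one regimen for the pantoprazole arm: "all patients randomised to the experimental group will be given intravenous pantoprazole 40 mg upon randomisation and hereafter once daily". Under section 3.5 it continues until ICU discharge or death in the ICU, up to 90 days after randomisation.

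**Eligibility.** One qualifying risk factor in section 4.1, taken from the medical history, is "History of chronic liver disease (portal hypertension, cirrhosis proven by biopsy, computed tomography (CT) scan or ultrasound, history of variceal bleeding or hepatic encephalopathy". It has no upper limit of severity. Section 4.2 excludes contraindications to PPI, which Appendix 4 defines narrowly: "Contraindications to proton pump inhibitors (PPI): any history of intolerance to PPI or additives or treatment with atazanavir (HIV medication"). No other exclusion concerns the liver. History of liver disease is a pre-planned subgroup in protocol section 11.2.1 and in the SAP, so such patients are expected.

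**Product text.** Appendix 5, section 4.2: "A daily dose of 20 mg pantoprazole (half a vial of 40 mg pantoprazole) should not be exceeded in patients with severe liver impairment". Section 4.4 asks for enzyme monitoring in the same patients and adds: "In the case of a rise in the liver enzymes, the treatment should be discontinued".

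**Amendments.** Amendments 1 and 2 concern Danish consent, and Amendment 3 cancels the second interim analysis. None touches the dose.

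**The concern.** The protocol appends a document that limits the dose in a definable group, leaves that group eligible, and then prescribes a higher dose for everyone without comment. The only rationale in section 6.1, securing systemic uptake, explains the intravenous route and not the dose in liver disease.

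It reads as an oversight because the product text sets the same 20 mg ceiling for co-treatment with atazanavir. The protocol deals with that case by excluding those patients, and leaves the hepatic ceiling unaddressed.

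At stake is consistency on patient safety. Most participants cannot consent for themselves at enrolment, and the staff are blinded, so a clinician who knows the limit cannot tell from the masked vial whether it is being exceeded.

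**Working it through.** The plan gives no figure on this point, so there is none to reproduce. The check sets the texts side by side and adds simple arithmetic.

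**1. Can a patient with severe liver impairment be randomised?** Yes. Section 4.1 admits cirrhosis and past hepatic encephalopathy or variceal bleeding. It also admits an INR above 1.5 by a separate route. Section 4.2 and Appendix 4 remove none of these patients on hepatic grounds. A history of chronic liver disease is not the same as severe impairment, so the clash covers only part of that group.

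**2. Dose against limit.** 40 mg / 20 mg = 2.

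**3. Is there a rule elsewhere?**
- Section 3.3.1.1 allows unblinding of an individual patient for treatment and safety.
- Section 5.2 provides written and oral site instructions and a 24-hour hotline.
- Section 4.3.2 allows stopping for intolerable reactions and requires it after a serious adverse reaction. Appendix 4 counts acute hepatic failure as one.
- Appendix 6 says that enzyme rises are not registered.

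The first two are available before any harm occurs. None of the four sets a dose.

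**4. What do the exposure data say?** Appendix 5, section 5.2, reports for Child A and B cirrhosis an AUC 5 to 7 times that of healthy subjects, a Cmax 1.5 times, and a half-life of 7 to 9 hours. Once-daily accumulation is 1/(1 − 2^(−24/t)):
- t = 7 h: 1/(1 − 0.0929) = 1.10
- t = 9 h: 1/(1 − 0.1575) = 1.19

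The overdose section (4.9) states: "Systemic exposure with up to 240 mg administered intravenously over 2 minutes was well tolerated". That is 240/40 = 6 times the trial dose. Section 5.2 also reports about 6 times the AUC in poor metabolisers, with no consequence for dosing.

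**5. What would 20 mg deliver?** Section 5.2 gives linear kinetics from 10 to 80 mg. Scaling the Child A/B figures, relative to a healthy subject on 40 mg:
- Cmax: 0.5 × 1.5 = 0.75
- AUC: 0.5 × 5 = 2.5 to 0.5 × 7 = 3.5

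**6. Can the dose be halved under blinding?** 40 mg in 10 ml is 4 mg/ml, so 20 mg is 5 ml. Placebo is prepared to the same volume: "Saline (10 ml) will be added to the empty vial in the same way as for the experimental intervention". Drawing 5 ml in both arms therefore looks the same.

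**The case against.** The strongest reply is that the hepatic limit is one of several places where the trial goes beyond the product text. Stress ulcer prophylaxis is not a listed indication, and the intravenous data cover up to 7 days, against up to 90 days in the trial. The protocol uses that text mainly for adverse reactions and expectedness, not as its dosing authority. Much of the exposure evidence is also reassuring: Cmax rises only modestly, accumulation is small, and high single exposure was tolerated. All this stands, and it keeps the point small. It does not close the gap. None of those figures is for severe impairment, and the text that contains them still sets 20 mg.

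A reader might infer four stronger things that the documents do not support:
- *Every patient enrolled with liver disease is overdosed.* The limit applies to severe impairment, which the product text does not define.
- *40 mg harms these patients.* No harm estimate is given in either direction.
- *The trial's safeguards operate only once harm has occurred.* Individual unblinding, the hotline and the site instructions do not wait for harm.
- *The trial needs an automatic stop on any enzyme rise.* Without a threshold, critical illness would trigger stops in both arms and dilute the treatment contrast in the liver subgroup, where the SAP hypothesises a larger effect.

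It is also fair to say that a stated reason for 40 mg, or an exclusion like that for atazanavir, would remove the inconsistency. The half-volume rule is a preference among workable remedies.

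**Conclusion.** The inconsistency is real and narrow. As written, the protocol gives eligible patients with severe liver impairment twice the daily maximum in its own appendix, and the protocol and SAP state no dose rule, exclusion or reason. The number affected cannot be derived from the documents, and the harm is not quantified. The primary estimate, the sample size and the type I error are not affected.

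The conclusion assumes that the site instructions, which are not part of these documents, contain no hepatic dose rule. If they do, the remedy is only to bring it into the protocol. Severity is minor to should-fix, as a patient-safety consistency point.

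**What to change.** 1. **Sections 6.1 and 6.2.** Add: patients with severe liver impairment, as judged by the treating clinician, receive 5 ml of the 10 ml reconstituted blinded solution once daily (20 mg pantoprazole or placebo); the rest is discarded.
2. **Appendix 4.** State what prompts that judgement: a baseline SOFA liver score of 3 or 4 (bilirubin 102 µmol/l or more in Appendix 10) in a patient with a history of chronic liver disease. This cut-off is a proposal. It uses bilirubin already collected at baseline. The plan collects no bilirubin after that, so later decisions rest on clinical judgement alone.
3. **Section 4.3.2.** Refer clinicians to product text section 4.4 and leave stopping to their judgement. Do not add an automatic enzyme stop without a threshold.
4. **eCRF and report.** Record full or half volume, and report the number on half volume per arm.

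**Cost.** An amendment with approvals, site training and added eCRF recording. Eligibility, sample size, allocation and vial supply do not change, since one vial a day is still used. Acid suppression may be weaker at 20 mg: Appendix 5, section 5.1, says "The inhibition is dose-dependent and affects both basal and stimulated acid secretion". The scaled Cmax of 0.75 points that way and the scaled AUC of 2.5 to 3.5 points the other way; neither figure is for severe impairment. The liver-subgroup estimate would describe the dose-adjusted regimen. If the rule were adopted mid-trial it would describe a mix of two regimens, which is a real consideration because the latest amendment is dated June 2017 and last enrolment was planned for November 2017. If the sponsor has grounds for 40 mg in these patients, the least change is to state them in section 6.1, although the limit would then still be exceeded.
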